9.7.14. Unscheduled Safety Visit

The Investigator may schedule an at-clinic Unscheduled/Safety Visit at any time if clinically warranted. Unscheduled and/or repeat assessments, including additional laboratory tests or investigations, may be conducted.

As appropriate, the Medical Monitor should be contacted.

10. INVESTIGATIONAL PRODUCT MATERIALS AND MANAGEMENT

10.1. Investigational Product

The investigational product is a white, round, film coated tablet containing OCA 5 mg or 10 mg or matching placebo. The tablets contain the following inactive ingredients: microcrystalline cellulose, sodium starch glycolate, and magnesium stearate.

10.2. Investigational Product Packaging and Labeling

The packaging and labeling of investigational product supplies will be performed according to Good Manufacturing Practice standards by a designated qualified vendor. All investigational product will be provided as tablets for oral administration and provided in high density polyethylene bottles with heat induction seals and child resistant closures. The bottle packaging will not reveal any information about the treatment dose contained in the bottle. Multiple bottles may be dispensed to the patient at each visit to provide enough tablets for dosing until the next visit.

The designated investigational product packaging/distribution vendor will also be responsible for the distribution of the investigational product to the Investigator.

10.3. Investigational Product Storage

All OCA tablet strengths provided to clinical study sites in support of clinical studies are to be shipped and stored at 15°C to 25°C. Temperature excursions within the range of 2°C and 30°C for no more than a 6-month period are acceptable, and the OCA tablet continues to be suitable for use in clinical studies. Additionally, temperature excursions within the range -20°C to 40°C for no more than 7 days are acceptable, and the OCA tablet continues to be suitable for use in clinical studies.

10.4. Investigational Product Administration

Refer to [Section 9.1](#).

10.5. Investigational Product Accountability and Disposal

The Sponsor's representative will send investigational product to the study site under appropriate storage conditions. All shipments of investigational product should be unpacked and the contents reviewed immediately upon receipt. If it is not possible to verify the contents immediately, they must be stored under the appropriate storage conditions until verification of the contents is possible (ideally, within 1 business day from receipt). The pharmacist or designee should verify the investigational product against the shipment documentation. The pharmacist or designee should contact the Sponsor immediately to report any concerns regarding the shipment.

All investigational product will be provided for use only in this study and is not to be used for any other purpose. The Investigator or designee will maintain a full record of investigational product accountability, including records of individual patient dispensing and final return or disposition (as directed by the Sponsor).

The study monitor, also known as the Clinical Research Associate (CRA), will review accountability records against investigational product dispensed and that remaining in stock, during on site monitoring visits and when the study is completed, or if it is prematurely terminated. The CRA will retrieve documentation detailing and confirming the return or destruction of the investigational product. If the investigational product is to be returned to the Sponsor's vendor for destruction, the CRA will also prepare the investigational product for shipment.

11. OVERVIEW OF ASSESSMENTS

The assessments supporting the objectives for the study are in Table 7:

Table 7: Table of Assessments

Primary Objectives	Assessments
PK parameters	OCA and its conjugates glyco-OCA and tauro-OCA, and metabolite OCA glucuronide
Safety and tolerability	SAEs and TEAEs, physical exam, ECG, vital signs, clinical laboratory assessments, discontinuations, pruritus, and fatigue
Secondary Objectives	Assessments
Changes in risk scores	Changes in MELD and in CP Scores and components of the CP score and MELD score
Changes in liver biochemistry and hepatobiliary damage	Total and direct bilirubin, ALP, ALT, AST, GGT, INR, creatinine, albumin, platelets
PD parameters	FGF-19, C4, and plasma bile acids
Additional Objectives	Assessments
Noninvasive measurements of liver fibrosis, liver stiffness and cirrhosis	TE/ELF (HA, P3NP, and TIMP-1)
PK/PD relationship	PK parameters compared to PD parameters and safety and tolerability assessments (above)
Patient-reported outcomes	Pruritus VAS, PBC-40, EQ-5D-5L, CLDQ
Clinical events	Death (all-cause and liver-related), liver transplant, MELD score ≥ 15 (for patients with MELD ≤ 12 at baseline), hospitalization for new onset or recurrence of: variceal bleed, hepatic encephalopathy, spontaneous bacterial peritonitis, uncontrolled ascites, and HCC.

ALP = alkaline phosphatase; ALT = alanine aminotransferase; AST = aspartate aminotransferase; C4 = 7 α -hydroxy-4-cholesten-3-one; CLDQ = Chronic Liver Disease Questionnaire; CP = Child-Pugh; ECG = electrocardiogram; ELF = enhanced liver fibrosis; FGF-19 = fibroblast growth factor-19; GGT = gamma-glutamyl transferase; HA = hyaluronic acid; INR = international normalized ratio; MELD = Model End Stage Liver Disease; OCA = obeticholic acid; P3NP = procollagen 3 N-terminal peptide; PBC = Primary Biliary Cholangitis; PD = pharmacodynamic; PK = pharmacokinetic; SAE = serious adverse event; TE = Transient Elastography; TEAE = treatment emergent adverse events; TIMP-1 = tissue inhibitor of metalloproteinase 1; VAS = visual analog scale

12. CLINICAL PHARMACOKINETIC ASSESSMENTS

Pharmacokinetic analyses will be based on the PK population (Section 15.1). Patients in the PK Population with at least one PD assessment after dosing will be included in the combined PK/PD analyses.

12.1. Pharmacokinetic Blood Sampling

Serial and fasting PK assessments will be performed in all patients participating in the study.

[figure not shown]
At Day 1, and Weeks 6, 12, 18, 24, 30, 36, and 48, patients will provide fasted blood samples for measurement of OCA and its conjugates, glyco-OCA and tauro-OCA, and metabolite OCA glucuronide 30 minutes before administration of investigational product (Table 8). Patients will then receive a dose of investigational product with approximately 240 mL of water.

Week 6 Visit should occur 3, 4, or 5 days **after** the Week 6 dose (eg, if the Week 6 dose of investigational product is taken on a Sunday, the patient should come in for the Week 6 Visit between Wednesday and Friday [Figure 3]).

During the treatment period:

- Pharmacokinetic fasting samples will be obtained from all patients at Day 1, and Weeks 6, 12, 18, 24, 30, 36, and 48 prior to dose administration in accordance with Figure 4.
- Serial PK assessments will be performed in all patients at Weeks 12, 18, 24, 30, and 48.

[figure not shown]
Figure 3: Week 6 Sampling Schedule

Week 6 Visit should be scheduled 3 to 5 days after the Week 6 OCA dose for collection of a single steady-state fasting PK sample

IP = investigational product; PK = pharmacokinetic

At Weeks 12, 18, 24, 30, and 48, serial PK blood samples will be obtained at 0.5, 0.75, 1, 1.5, 2, 2.5, 3, 4, 5, 6, 7, 8, 9, and 24 hours postdose (Figure 4) for all patients. The patient will be given the option to return to the clinic the following morning for the 24-hour postdose sample or samples can be obtained by a home health care designee. The home health care agency must be advised one week in advance of the appointment.

Figure 4: Pharmacokinetic Sampling Schedule

At meal timepoints, meals are consumed immediately after the collection of the PK sample

h = hour; IP = investigational product; PK = pharmacokinetic

Patients should not drink additional water for 1 hour after taking the dose of investigational product and will remain fasted until after the 1-hour sample is collected. A meal replacement drink will be provided following collection of the 1-, 4-, and 7-hour PK sample. The nutritional information of the meal replacement drink should be submitted to and approved by the Sponsor in advance. No other food or drink (water is permitted) will be allowed until after the 9-hour sample collection.

Table 8: Acceptable Windows for Pharmacokinetic Sample Collection

Nominal Sampling Time	Acceptable Sampling Window
Before administration of investigational product (predose or fasting)	Within 30 minutes before dosing
0.5 to 1.5 hours after investigational product	± 10 minutes
2 to 2.5 hours after investigational product	± 20 minutes
3 to 24 hours after investigational product	± 30 minutes

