7.3. Planned Dosing Regimen

All patients will initiate investigational product once weekly with OCA 5 mg or matching placebo (Table 2). Titration may be considered as early as the Week 12 Visit. Following visit procedures at Week 12, if the investigational product is tolerated and laboratory assessments do not indicate a safety concern, the patient may up-titrate to OCA 5 mg twice weekly and may start the higher dose regimen no earlier than 2 days after they took their last dose. Dosing will then occur at least 3 days apart. Every 6 weeks thereafter, based on tolerability assessments, patients can be considered for further up titration as described below (Table 2). At each titration visit, the patient may start the higher dose regimen no earlier than 2 days after the prior dose.

Patients may titrate to a maximum dose of OCA 10 mg twice weekly at least 3 days apart.

Table 2: Planned OCA or Matching Placebo Dosing Regimen

	Child-Pugh B and Child-Pugh C (Moderate and Severe Hepatic Impairment)	
	Treatment Group	
	OCA	Placebo
Starting Dose (Day 1)	5 mg once weekly	matching placebo once weekly
Titration 1 ^a	5 mg twice weekly ^b	matching placebo twice weekly ^b
Titration 2 ^a	10 mg twice weekly ^b	matching placebo twice weekly ^b

^a Planned titration regimen is shown; however, the titration of dose and/or frequency is dependent on patient tolerability.

^b Dosing per the twice weekly schedule must be at least 3 days apart.

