9.7.7. Week 6 Procedures

Week 6 Visit should occur 3, 4, or 5 days after taking the Week 6 dose, eg, if the Week 6 dose is taken on a Sunday, the patient should come in for the Week 6 Visit within the following Wednesday and Friday ([Figure 3](#)).

- Verify that the patient has fasted for at least 8 hours.
 - Record fasting status in the source and eCRF
 - If the patient reports having eaten within 8 hours, document accordingly in the source and eCRF and remind the patient that fasting is required prior to all study visits, but water is permitted.
- Assess and record vital signs and weight (oral temperature, sitting heart rate, respiratory rate, and sitting blood pressure).

- Assess and record AEs.
- Review and record concomitant medications.
- Perform a physical examination.
- Review and record any non-study related medical or surgical treatment procedures and any medically relevant HCP or non-HCP related office visits that have occurred since the previous study visit.
- Perform assessments for calculation of CP Score ([Section 14.1.1](#)).
- Administer Quality of Life and Patient questionnaires (see [Section 13.2.7](#)).
- Assess investigational product compliance, perform investigational product accountability.
- Perform a urine-based β -hCG pregnancy test in females of childbearing potential.
- Obtain blood samples for
 - Serum chemistry, hematology, and coagulation
 - Bile Acids/C4/FGF-19
 - Fasting PK assessment
- Schedule the next visit, reiterate dosing instructions, and advise the patient:
 - NOT to take investigational product on the morning of the next visit, and
 - To bring the investigational product bottle(s); s/he will dose at the clinic (if this is in compliance with the established dosing frequency), and
 - To fast overnight (at least 8 hours) prior to the next visit. Fasting is required prior to all study visits, but water is permitted.

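### Section 12.1 has a dose follow the fasted sample at every PK visit, including Week 6 and Week 36, which contradicts the Week 6 timing, the once-weekly regimen and the visit procedures

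*Protocol*

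**What the plan says.** Protocol Section 12.1 opens with one general instruction. "At Day 1, and Weeks 6, 12, 18, 24, 30, 36, and 48, patients will provide fasted blood samples", the sample being timed 30 minutes before product is administered, and then: "Patients will then receive a dose of investigational product with approximately 240 mL of water". Week 6 and Week 36 are both in the list and neither is excepted. A bullet later in the section again describes the fasting samples at all these visits as pre-dose. Table 8 treats predose and fasting samples as one category, with a window set by the dose that follows.

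On Week 6 specifically, Section 9.7.7 states: "Week 6 Visit should occur 3, 4, or 5 days after taking the Week 6 dose". Section 12.1 repeats this, and its Figure 3 caption says the visit is "scheduled 3 to 5 days after the Week 6 OCA dose for collection of a single steady-state fasting PK sample".

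On the regimen in force, Section 7.3 states: "All patients will initiate investigational product once weekly with OCA 5 mg or matching placebo". It adds: "Titration may be considered as early as the Week 12 Visit".

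On procedures, Section 9.7.7 lists a fasting PK sample at Week 6 and no step to give product. Section 9.7.9 puts administration under the serial PK assessment, which it limits to Weeks 12 and 24 and excludes at Week 36. Table 1 marks fasting PK collection at Day 1, Week 6 and Week 36, and serial collection at Weeks 12, 18, 24, 30 and 48.

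**The concern.** The sentence in 12.1 is an instruction to administer drug, not a description of an analysis. It sits in the section that staff would open to run a PK visit. At Week 6 the weekly dose has already been taken, by design, so a dose after the sample would fall outside the once-weekly schedule and before titration may be considered. The patients have Child-Pugh B or C disease, and Section 5.5 stresses close monitoring because of their decompensation risk and potentially higher hepatic exposure.

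The setting makes a misreading possible. Section 9.7.6 tells patients at Week 3 not to take product on the morning of the Week 6 visit and to bring the bottle, so they arrive fasted and carrying drug. The proviso that a clinic dose must fit the established dosing frequency appears in Section 9.7, where in 9.7.7 it concerns the following visit. It does not appear in 12.1.

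The sample definition is affected too. If no dose follows the Week 6 sample, the Table 8 window has no reference time at that visit.

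**Working it through.** The protocol gives no figure to reproduce here. The check compares the passages and applies interval arithmetic.

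**Passages side by side**

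| Source | Week 6 | Week 36 |
|---|---|---|
| 12.1, general sentence | sample, then dose | sample, then dose |
| 12.1, fasting-sample bullet; Table 8 | sample defined relative to a following dose | same |
| 12.1, Week 6 paragraph and Figure 3 caption | visit 3 to 5 days after the dose; single fasting sample | not addressed |
| 7.3 | once-weekly dosing | depends on titration |
| 9.7.7 / 9.7.9 | fasting sample, no administration step | fasting sample; administration tied to serial PK, not done |
| Table 1 | fasting PK only | fasting PK only |

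The first two rows disagree with the procedure sections at both visits. At Week 6 they also disagree with 12.1's own timing and with 7.3.

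**Interval arithmetic for Week 6**

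Inputs: dosing interval 7 days (Section 7.3, once weekly); OCA dose 5 mg (Section 7.3); visit at d = 3, 4 or 5 days after the dose (Sections 9.7.7 and 12.1); earliest titration Week 12 (Section 7.3).

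Days from a clinic dose to the next regular weekly dose = 7 − d:

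- d = 3: 7 − 3 = 4 days
- d = 4: 7 − 4 = 3 days
- d = 5: 7 − 5 = 2 days

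Case A, the weekly day is kept. The interval contains 2 doses instead of 1. On OCA that is 2 × 5 mg = 10 mg instead of 5 mg, the same number of doses per week as Titration 1 in Table 2. It comes 12 − 6 = 6 weeks before titration may first be considered. With d = 5 the gap to the next dose is 2 days. For comparison only, since that rule governs the later regimen, Table 2 says: "Dosing per the twice weekly schedule must be at least 3 days apart".

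Case B, the site moves the weekly day to the visit day. No additional dose falls in the interval, but the dose is 2 to 4 days early (7 − 5 to 7 − 3). Nothing in the protocol instructs this move.

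**Week 36**

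No offset from the regular dose is specified. A clinic dose could coincide with the patient's dosing day, so the difference between 12.1 and 9.7.9 concerns whether a dose is given in clinic, not necessarily an extra dose.

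**The case against.** The best reply is that the protocol, read as a whole, leans one way on Week 6. The Week 6 rule comes directly after the general sentence and can be read as qualifying it. The Week 6 checklist has no administration step, whereas the serial PK visits have an explicit one with the volume of water. Table 1 has no dispensing mark at Week 6. Section 9.1 speaks of visits where product is given at the site, which implies that not every visit is one. In Section 9.7.6 the Week 42 instruction mentions dosing at the clinic and the Week 3 instruction does not. The Version 3 summary of changes, useful here only as evidence of intent, gives as a reason that clinic dosing belongs to serial PK visits. Figures 3 and 4 are not shown and might settle the matter on the page.

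This stands as far as likelihood goes: a site working from 9.7.7 would not dose at Week 6. It does not remove the contradiction. The general sentence has no exception, and the bullet and Table 8 repeat its premise.

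Stronger readings are tempting and are not supported. A reader might infer that all of the roughly 25 OCA patients (50 randomized 1:1) would take an extra dose. That is only a ceiling, requiring every site to put one sentence above the checklist. A reader might also infer that the Week 12 profile would be distorted. It comes six weeks later, and the protocol gives no half-life or carry-over figure to support this.

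**Conclusion.** The contradiction is real and lies in current text. As written, 12.1 cannot be followed together with its own Week 6 timing, Section 7.3 and Section 9.7.7. Its size for a patient is one off-schedule dose, 3 to 5 days into a 7-day interval. It is additional (two doses in the interval) if the weekly day is kept, and early if the day is moved. At Week 36 the text conflicts only on whether a clinic dose is given, and an extra dose should not be inferred there.

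This rests on a literal reading of 12.1 and on patients still being on the once-weekly regimen at Week 6, as Section 7.3 provides. How many sites would act on 12.1 cannot be estimated from the protocol. Because the sentence instructs drug administration in Child-Pugh B and C patients, it deserves correction even though the other sections make the misreading less likely. The conclusion takes no position on which dosing instruction is right.

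**What to change.** Reconcile three places in Section 12.1 (the general dosing sentence, the bullet describing fasting samples as pre-dose, and the combined predose/fasting row of Table 8) with Sections 7.3, 9.7.6, 9.7.7 and 9.7.9 and Table 1. The protocol should then say the same thing everywhere, visit by visit, about whether investigational product is administered in clinic. For any visit without a clinic dose, the reference time for the fasting sample should be stated. Figures 3 and 4 should be checked against the result. Which instruction prevails is for the sponsor's clinical and pharmacology team to decide. The cost is a wording amendment and a note to sites, with no added visits, samples or procedures. No change to the PK analysis rules is needed to resolve this point; handling of off-schedule samples belongs in the SAP.

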12.2. Processing and Handling of Pharmacokinetic Samples

Whole blood will be collected at each scheduled sample timepoint. Detailed procedures for the collection of blood samples including further processing into plasma will be provided in a separate laboratory manual. The storage and shipment procedures for subsequent bioanalysis, will be provided to the investigational site and home health care company in a separate document before the study is initiated.

12.3. Bioanalysis

Plasma concentrations of OCA and its conjugates, glyco-OCA and tauro-OCA, and metabolite OCA glucuronide will be determined using a validated liquid-chromatography mass spectrometry/mass spectrometry (LC/MS/MS) method. A detailed description of validation information and results from the bioanalytical assay will be provided in separate reports. These samples may be used for evaluation of metabolites of OCA or other concomitant medication, for further evaluation of the bioanalytical method, and for analyses that provide information on the metabolic pathways used or impacted by OCA.

13. ASSESSMENT OF SAFETY

13.1. Adverse Events and Serious Adverse Events

13.1.1. Definitions of Adverse Events

13.1.1.1. Adverse Event

AEs are defined as any untoward medical occurrence associated with the use of the investigational product in humans, whether or not considered related to investigational product. An AE, also referred to as an adverse experience, can be any unfavorable and unintended sign (eg, an abnormal laboratory finding), symptom, or disease temporally associated with any use of the investigational product, without any judgment about causality and irrespective of route of administration, formulation, or dose, including an overdose.

AEs include, but are not limited to: (1) a worsening or change in nature, severity, or frequency of condition(s) present at the start of the study; (2) patient deterioration due to primary illness; (3) intercurrent illness; and (4) drug interaction. For reporting purposes, pregnancy is not considered an AE.

Patients should be questioned about AEs in a general way, without leading the patient or asking about the occurrence of any specific symptom. The Investigator should attempt to establish a diagnosis of the event based on signs, symptoms, and/or other clinical information. The diagnosis and not the individual signs/symptoms should be documented as the AE. For example, if the underlying disease process is a stroke, it would not be appropriate to record the AE by describing the symptoms “sudden numbness, dizziness, and difficulty speaking.” The AE medical term of “stroke or cerebrovascular accident” should be recorded as it more accurately describes the AE.

Patients should be instructed to contact the site promptly upon awareness if they develop signs and symptoms of potential hepatic decompensation such as: pale-colored stools, urine color from pale to deep amber [dark], nausea, vomiting, abdominal pain, diarrhea, weight loss, fever and chills, fatigue, weakness, loss of appetite, confusion, swelling of the legs or abdomen, yellowing of the skin or the whites of eyes, and bruising easily.

13.1.1.2. Serious Adverse Event

An AE is considered “serious” if, in the view of either the Investigator or Sponsor, it results in any of the following outcomes:

- Death
- Is immediately life threatening
- Requires in-patient hospitalization or prolongation of existing hospitalization
- Results in persistent or significant disability or incapacity
- Results in a congenital abnormality or birth defect
- Is an important medical event that may jeopardize the patient or may require medical intervention to prevent one of the outcomes listed above.

Events **not** considered to be SAEs are hospitalizations for:

- Routine monitoring of the studied indication and not associated with any deterioration in condition or AE;
- Elective treatment for a pre-existing condition that did not worsen;
- Respite care or observation when there is no AE associated with the hospitalization.

